12.12 Day 197 (± 7) – End of Study

- 1) CCI to be self-administered by the subject via their personal electronic device.
- 2) Document any changes to health status.
- 3) Document any changes to concomitant medications.
- 4) Document any changes to baseline diet.
- 5) Determine body weight.
- 6) Obtain vital signs before blood draws.
- 7) Perform symptom-directed physical exam, as needed.
- 8) Collect the following samples for the central laboratory:
 - a) CBC with differential – blood counts determine if extended follow-up is required.
 - b) Chemistry
 - c) Pharmacokinetics
 - d) Anti-drug antibodies
 - e) Blood for exploratory analysis
 - f) Urinalysis

12.13 Early Termination

Perform 28 (± 3) days after the last dose of study drug (or before, if necessary, to ensure compliance with the visit). If a subject discontinues the study more than 28 days after the last dose of study drug, the ET visit should be performed as soon as possible.

- 1) *If early termination occurs after Day 29 and prior to Day 169*, the subject should arrive fasting for the EGD procedure, as specified by instructions from the EGD provider.
- 2) **CCI** to be self-administered by the subject via their personal electronic device.
- 3) Document any changes to health status.
- 4) Document any changes to concomitant medications.
- 5) Document any changes to baseline diet.
- 6) Determine body weight.
- 7) Obtain vital signs before blood draws.
- 8) Perform symptom-directed physical exam, as needed.
- 9) Collect the following samples for the central laboratory:
 - a) CBC with differential – blood counts determine if extended follow-up is required.
 - b) Chemistry
 - c) Pharmacokinetics
 - d) Anti-drug antibodies
 - e) Total Serum IgE *only if early termination occurs prior to Day 169*
 - f) Blood for exploratory analysis
 - g) Urinalysis
- 10) Perform EGD *only if early termination occurs after Day 29 and prior to Day 169*.
 - a) Assess and grade endoscopic severity per the EREFS using the EREFS Scoring Tool.
 - b) Biopsy collection per the AK002-014 Histology Manual, Central Laboratory Manual, and all EGD facility SOP.

12.14 Extended Follow-Up

Subjects must return to the site every 28 (± 3) days to monitor absolute lymphocyte and eosinophil counts until recovery. Data collected during extended follow-up will be limited to:

- 1) CBC with differential
- 2) Adverse events of special interest
- 3) Serious adverse event

13. Adverse Event Reporting and Documentation

13.1 Adverse Events

In accordance with 21 Code of Federal Regulation (CFR) 312.32(b) and International Conference on Harmonisation (ICH) Guidance E2A, an adverse event is any untoward medical occurrence in a clinical investigation of a subject administered a pharmaceutical product and that does not necessarily have a causal relationship with the treatment. An AE is therefore any unfavorable and unintended sign (including an abnormal laboratory finding), symptom, or disease temporally associated with the administration of an investigational product, whether or not related to that investigational product. An unexpected AE is one of a type not identified in nature, severity, or frequency in the current Investigator's Brochure or of greater severity or frequency than expected based on the information in the Investigator's Brochure.

Examples of an AE include:

- Significant worsening or exacerbation of an underlying medical condition.
- Significant abnormal findings from physical exams, vital signs, or laboratory tests.

The following examples are not considered an AE:

- Medical or surgical procedure, although the condition leading to the procedure is usually an AE.
- Anticipated day-to-day fluctuations of preexisting medical conditions (including laboratory values) as long as significant worsening from Baseline does not occur.
- Signs or symptoms of the disorder being studied unless they become more severe or occur with a greater frequency than occurring at Baseline.

All AE, whether elicited by questions from study staff, volunteered, or noted on physical examination/laboratory testing, and regardless of causality or severity, will be assessed and recorded in the eCRF beginning after first administration of study drug and ending at the time of the Day 197 visit, the Day 372 visit (for subjects participating in the OLE period), or the ET visit, unless otherwise directed by Allakos. For subjects participating in the OLE period, AE will be assessed and recorded in the CRF of the AK002-014 treatment period database up until the start of the first open-label infusion during the Day 176 visit and recorded in the CRF of the

AK002-014 OLE period database beginning from the start of the first open-label infusion during the Day 176 visit.

13.2 Serious Adverse Events

A serious adverse event (SAE) is defined as an AE that meets one of the following criteria:

- Death
- A life-threatening AE that places the subject at risk of death at the time of the event. It does not refer to an event that hypothetically might cause death if it were more severe.
- Inpatient hospitalization or prolongation of existing hospitalization.
- A persistent or significant disability/incapacity.
- A congenital anomaly/birth defect occurring in the offspring of a study subject.
- Other important medical events may also be considered an SAE when, based on appropriate medical judgment, they jeopardize the subject or require intervention to prevent one of the outcomes listed above.

SAE will be assessed and recorded after the first administration of study drug and ending at the time of the Day 197 visit, the Day 372 visit (for subjects participating in the OLE period), the ET visit, or the last Extended Follow-Up visit (if applicable), unless otherwise directed by Allakos. If an SAE that occurs during the screening period (after consent and before the first administration of study drug) is assessed to be related to a screening procedure, it will also be recorded.

13.3 Adverse Events of Special Interest

Adverse events of special Interest (AESI) for this study include:

- Malignancies confirmed by histopathological report. (Mast cells and eosinophils are part of the normal immune response. By decreasing their function, AK002 could theoretically increase the risk of malignancy.)
- Parasitic infections confirmed by positive clinical laboratory test. (Eosinophils are especially active in protecting the body from parasitic infections and decreasing their function could theoretically increase the risk of parasitic and opportunistic infections.)
- Opportunistic infections (infections known to be more severe or occur more frequently in immunosuppressed populations) as confirmed by positive clinical laboratory test.
- Infusion-related reactions and hypersensitivity reactions including anaphylaxis.

Beginning from the time of first study drug infusion and ending at the time of the Day 197 visit, the Day 372 visit (for subjects participating in the OLE period), the ET visit, or the last extended follow-up visit (if applicable), any new AESI (or new information related to a previously reported AESI) must be recorded in the Adverse Event eCRF and designated as an “adverse event of special interest.”

For subjects participating in the OLE period, AESI will be assessed and recorded in the CRF of the AK002-014 treatment period database up until the start of the first open-label infusion during the Day 176 visit and recorded in the CRF of the AK002-014 OLE period database beginning from the start of the first open-label infusion during the Day 176 visit.

13.4 Infusion-Related Reactions

All AE considered by the Investigator to be related to the infusion of the biological substance and occurring within 24 hours of the start of the study drug infusion should be captured as 1 IRR. Common symptoms of IRR include but are not exclusive to:

- Flushing
- Chills
- Back or abdominal pain
- Chest discomfort or tightness
- Dizziness
- Shortness of breath
- Headache
- Hypotension or hypertension
- Nausea
- Vomiting
- Sweating
- Fever
- Urticaria
- Pruritus
- Bronchospasm

All symptoms experienced by a subject during an IRR will be listed in the eCRF under 1 IRR, unless the Investigator believes a symptom is not part of the IRR, in which case it will be recorded separately. The start time of the IRR will be captured as the start time of the first symptom, and the end time of the IRR will be captured as the end time of the last symptom.

If the subject experiences an IRR that causes an interruption or cessation of the study drug infusion, a blood sample should be collected within 1–2 hours of the onset of symptoms for exploratory safety analysis.

Subjects will remain at the site for at least 1 hour of observation after each dose. If the subject experiences an IRR, prolonged observation (greater than 1 hour or until the symptoms resolve)

may be required, as per Investigator discretion. Subjects will also be instructed to immediately contact the study doctor if any reactions occur after discharge.

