2.3 Overview of Clinical Studies

AK002, administered as a monthly intravenous infusion, has previously been tested in healthy volunteers and in subjects with indolent systemic mastocytosis (ISM), chronic urticaria, severe allergic conjunctivitis (AC), mast cell gastritis, and eosinophilic gastritis (EG) and/or eosinophilic duodenitis (EoD), referred to as eosinophilic gastroenteritis (EGE) in previous studies.

Multiple doses of 3 mg/kg have been given to subjects with ISM, chronic urticaria, severe AC, mast cell gastritis, and EG and/or EoD. In these studies, AK002 pharmacodynamic (PD) activity was observed for prolonged periods of time and the AK002 pharmacokinetic (PK) parameters demonstrated a half-life amenable to administration every 4 weeks.

To date, 51 healthy volunteers (36 on AK002, 15 on placebo), 25 subjects with ISM, 47 subjects with chronic urticaria (including spontaneous and inducible), 30 subjects with severe AC, 8 subjects with mast cell gastritis, and 65 subjects with EG and/or EoD (43 on AK002 and 22 on placebo) have been enrolled in clinical studies.

In general, AK002 was well tolerated. The most common treatment-emergent adverse event (TEAE) observed was infusion-related reactions (IRR). Most IRR were mild to moderate and 2 IRR (1 in the healthy volunteer study and 1 in the AK002-003 study) were serious but resolved within 24 hours. Common symptoms of IRR were headache, nausea, sweating, flushing, and redness. Most IRR occurring during the infusion could be managed by slowing or temporary interruption of the infusion, with minimal intervention. In 6 healthy volunteers who received 2 doses of 0.3 mg/kg, 4 weeks apart, the second dose was better tolerated than the first dose. This is also the case in patients with ISM, chronic urticaria, severe AC, and EG and/or EoD; fewer adverse events (AE) were reported during the second and subsequent infusions when compared to the first infusion.

In all studies, a transient decrease in lymphocyte counts was observed after the AK002 infusion (usually resolving within 1 day) that was not associated with any clinical consequence, and a sustained depletion of eosinophils was observed that is consistent with the mechanism of action of AK002. No significant trends were observed for changes in vital signs, electrocardiograms (ECG), clinical laboratory parameters, or physical examinations.

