In the randomized, double-blind, placebo-controlled, Phase 2 study of AK002 in 65 subjects with EG and/or EoD, subjects were randomized to receive monthly doses of placebo, low dose AK002 (0.3, 1, 1, and 1 mg/kg), or high dose AK002 (0.3, 1, 3, and 3 mg/kg) in a 1:1:1 ratio. All primary and secondary endpoints were met in the study. There was a mean reduction of 97% and 92% in eosinophils in the stomach and duodenum at the high dose and low dose AK002-treated subjects, respectively, versus a 10% increase for placebo-treated subjects ($p < 0.0001$). The reduction of eosinophils was associated with a statistically significant reduction in total symptom score on 8 items (TSS8) of 58% in the high dose group, 49% in the low dose group versus 24% in the placebo group ($p = 0.0012$ and $p = 0.015$, respectively). Improvement in symptoms was observed within 24 hours of the first dose of study drug. In addition, 70% of high dose AK002-treated subjects and 68% of low dose AK002-treated subjects were treatment responders (defined as $>30\%$ improvement in TSS and $>75\%$ reduction from baseline in tissue eosinophils) versus 5% of placebo-treated subjects ($p < 0.0001$).

Approximately 40% of subjects had concomitant EoE. In those subjects, a mean reduction of 95% of eosinophils/hpf was observed in the esophageal biopsies of AK002-treated subjects versus no change on placebo. Also, 13 of 14 (93%) subjects with EoE on AK002 were histologic responders (defined by ≤ 6 eosinophils/hpf) versus 1 of 11 (9%) subjects with EoE on placebo. Dysphagia improved by 53% in AK002-treated subjects versus 17% in placebo-treated subjects.

AK002 was well tolerated with IRR being the only AE that occurred more frequently in AK002-treated subjects than in placebo-treated subjects.

More than 90% of subjects in the Phase 2 study elected to continue into a long-term continuation study. In the long-term, open-label continuation study, a starting dose of 1 mg/kg was used, followed by subsequent doses of 3 mg/kg. Premedication of 80 mg prednisone was administered the day before the first dose and second dose and, using this regimen, no IRR were reported for the first infusion of the continuation study.

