13.6 Evaluating Adverse Events and Serious Adverse Events

13.6.1 Establishing Diagnosis

Whenever possible, diagnoses should be given when signs and symptoms are due to a common etiology (e.g., dysuria, urinary nitrites should be reported as a urinary tract infection). If the diagnosis is not known, individual signs and symptoms should be assessed and recorded in the Adverse Event eCRF as separate AE. The Investigator (or qualified Subinvestigator) must assign the following AE attributes listed below and is responsible for ensuring their capture in the source documentation.

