## 6.15 Safety Analyses

### 6.15.1 Adverse Events

Safety assessments will be based mainly on the nature, frequency, relationship, and severity of the AE, and AE will be coded by primary SOC and PT according to MedDRA (version 21.0).

The treatment-emergent adverse events (TEAE) will be summarized by the number and percentage (n and %) of subjects in each SOC and PT.

For summaries by relationship to study drug, “possibly related” will be combined with “related”, and “unlikely/remotely related” will be combined with “not related.” When multiple AE are reported with the same PT, the AE of the strongest relation to study drug will be included in the summary by relationship, and the AE of the most severe grade will be included in the summary by severity table.

The following AE incidence tables will be presented.

- Overview of TEAE to include
  - Number (%) of subjects who reported at least 1 TEAE
  - Number (%) of subjects who reported at least 1 treatment-related TEAE
  - Number (%) of subjects who reported at least 1 severe TEAE
  - Number (%) of subjects who reported at least 1 serious TEAE
  - Number (%) of subjects who reported at least 1 TEAE leading to treatment discontinuation
  - Number (%) of subjects who reported at least 1 TEAE leading to study discontinuation
  - Number (%) of subjects who reported at least 1 TEAE of special interest (TEAESI)
- TEAE by PT sorted by decreasing order of subject incidence in the combined treatment group
- TEAE by SOC and PT in alphabetical order
- TEAE by SOC, PT, and maximum severity
- TEAE by SOC, PT, and strongest relationship to study drug
- TEAE leading to treatment discontinuation by SOC and PT, if warranted by sample size
- TEAE leading to study discontinuation by SOC and PT, if warranted by sample size
- Serious TEAE by SOC and PT, if warranted by sample size
- TEAESI by SOC and PT

All AE will be listed with onset/stop day, relationship to study drug, severity, action taken, and outcome. Pertinent subject information including treatment group and demographics will also be included.

Separate listings will be provided for TEAE leading to study discontinuation, TEAESI, and treatment-emergent SAE (TESAE).

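### Symptom rows in the adverse event tables omit infusion-attributed events, and no planned table counts those symptoms by arm

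*Protocol*

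**What the plan says.** Protocol 13.4 directs that adverse events which the Investigator relates to the infusion, "occurring within 24 hours of the start of the study drug infusion should be captured as 1 IRR". The components go beneath that event: "All symptoms experienced by a subject during an IRR will be listed in the eCRF under 1 IRR". The one exception is a symptom that, in the Investigator's judgment, does not belong to the reaction; it becomes an event of its own. The symptoms named in 13.4 include headache, nausea, vomiting, dizziness and fever as well as flushing, urticaria, hypotension and bronchospasm.

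This fits the general convention in Protocol 13.6.1: "Whenever possible, diagnoses should be given when signs and symptoms are due to a common etiology".

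SAP 6.15.1 then states: "The treatment-emergent adverse events (TEAE) will be summarized by the number and percentage (n and %) of subjects in each SOC and PT". The tables are an overview, incidence by preferred term (PT) and by system organ class (SOC) and PT, the same by maximum severity and by strongest relationship, and tables for discontinuations, serious events and events of special interest ("TEAESI by SOC and PT"). Appendix 3 carries these as Tables 14.3.1.1 to 14.3.1.8. None counts the symptoms inside an IRR, and the SAP does not say whether those symptoms are MedDRA-coded.

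On frequency, Protocol 2.3 reports of earlier AK002 studies: "Common symptoms of IRR were headache, nausea, sweating, flushing, and redness". Of the Phase 2 study in eosinophilic gastritis and duodenitis it says: "AK002 was well tolerated with IRR being the only AE that occurred more frequently in AK002-treated subjects than in placebo-treated subjects". It gives no IRR or symptom rates.

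**The concern.** A reader of an all-causality PT table takes the headache row to be the proportion of subjects who had a headache. Under these rules it is the proportion who had a headache that was not placed inside an IRR. Whether a headache is placed there depends on timing and on judged relation to the infusion. If IRRs are commoner on AK002, more headaches leave the headache row in the AK002 arms than on placebo, and the row shows a smaller difference than the subjects experienced.

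The same applies to the signs that matter for hypersensitivity. Protocol 13.3 puts IRRs and hypersensitivity reactions, including anaphylaxis, in one special-interest item. A special-interest table by SOC and PT shows how many subjects had an IRR, but not how many of those IRRs included urticaria, hypotension or bronchospasm. Adverse event incidence and severity are the stated safety objective (Protocol 4.4), and these tables are its main output.

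**Working it through.** The plan gives no figure on this point to reproduce. The check has two parts: follow a symptom through the rules, then size the effect under assumed rates.

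**Where one headache is counted**

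| Headache | Recorded as | Row in the planned tables |
|---|---|---|
| Within 24 hours of infusion start, judged part of an IRR | Listed under 1 IRR | IRR row only |
| Within 24 hours, judged not part of an IRR | Separate event | Headache row |
| Later than 24 hours | Separate event | Headache row |

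The first line assumes that only the IRR term is coded and counted. The SAP is silent on coding of the components, but no planned table would count them.

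**Size under assumed rates**

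All of these inputs are assumptions:
- b: risk of the symptom outside an IRR, the same in every arm (5% or 10%).
- a and p: risk of the symptom inside an IRR on AK002 and on placebo.
- The two sources are independent.

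Proportion with the symptom from any source: 1 − (1 − b)(1 − a) on AK002, and 1 − (1 − b)(1 − p) on placebo. The difference is (1 − b)(a − p). The PT row shows b in both arms, a difference of 0, so all of (1 − b)(a − p) is hidden from that row.

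| a | p | b = 5%: AK002 vs placebo | Hidden difference | b = 10%: AK002 vs placebo | Hidden difference |
|---|---|---|---|---|---|
| 3% | 3% | 7.85% vs 7.85% | 0 | 12.7% vs 12.7% | 0 |
| 5% | 2% | 9.75% vs 6.9% | 2.85 points | 14.5% vs 11.8% | 2.7 points |
| 10% | 2% | 14.5% vs 6.9% | 7.6 points | 19.0% vs 11.8% | 7.2 points |
| 20% | 4% | 24.0% vs 8.8% | 15.2 points | 28.0% vs 13.6% | 14.4 points |
| 30% | 5% | 33.5% vs 9.75% | 23.75 points | 37.0% vs 14.5% | 22.5 points |

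**A second set of assumptions**

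Write a and p as the IRR rate times the share of IRRs that include headache. Assume an IRR rate of 20-60% on AK002 and 5-15% on placebo, a share of 20-40% (the same in both arms), and b = 10%:
- Smallest difference: 0.9 × (0.20 × 0.20 − 0.15 × 0.20) = 0.9 points.
- Largest difference: 0.9 × (0.60 × 0.40 − 0.05 × 0.40) = 19.8 points.
- One case between, IRR 40% vs 5% and share 40%: a = 16%, p = 2%. Any-source headache is 24.4% vs 11.8%, a difference of 12.6 points, while the headache row shows 10% vs 10%.

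Here the AK002 excess is built in, because every assumed AK002 IRR rate exceeds every placebo rate. The figures illustrate size and are not evidence that the imbalance exists.

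**The case against.** The strongest case on the other side is that this is ordinary diagnosis reporting. Under 13.6.1 a diagnosis replaces its signs and symptoms. A headache row that excludes headaches belonging to a diagnosed IRR is correct for what it counts. The rule depends on timing and attribution, not on arm. Investigators are blinded (Protocol 10.3), and an attributed headache on placebo is folded in the same way. The IRR is itself a treatment-emergent event and an event of special interest, so it appears by arm in the overview, the PT and SOC/PT tables, the severity and relationship tables and the special-interest table. The symptoms are kept in the eCRF, and SAP 5.1 says that all eCRF data will be listed. Suspected anaphylaxis is assessed separately (Protocol 13.5). Safety analysis is descriptive (Protocol 15.1), so no test is affected.

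All of that stands, and it rules out two stronger readings. A reader might infer that these harms disappear from the adverse event tables, or that the tables give wrong incidences. They do neither: the harm moves to the IRR row, and an AK002-placebo difference in IRRs stays visible there. A reader might also infer that the Phase 2 statement, that only IRR was more frequent on AK002, is a product of such a recording rule. The documents do not describe how that study recorded adverse events, so this cannot be shown.

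The imbalance may also be small here. All subjects take prednisone before the first infusion, and the synopsis reports no IRR on infusions 1 and 2 in a premedicated subset of the extension study. That is limited reassurance. In that subset both doses were premedicated, whereas here only the first is. In the parent study 43 of 65 subjects had received AK002, and Protocol 2.3 reports fewer events at later infusions, whereas this trial excludes prior exposure.

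None of this supplies the missing information. The IRR row does not show which symptoms occurred, and subject listings for about 300 people do not give incidences by arm.

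**Conclusion.** The point holds as a gap in tabulation. As planned, the symptom PT rows exclude infusion-attributed events, and no table restores them by arm. These rows therefore understate any AK002-placebo difference by (1 − b)(a − p). That is zero if IRR symptoms are equally frequent in the arms, and a little over 20 points at the top of the assumed range. The direction rests on the IRR excess reported for the earlier study, and the size rests wholly on assumed rates. The conclusion also assumes that component symptoms are not coded and counted as separate events, on which the SAP is silent. Efficacy results and the testing hierarchy are untouched. What changes is what can be concluded about individual symptoms and hypersensitivity-type signs. It is a cheap improvement to reporting, not the correction of an invalid analysis.

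**What to change.** State in SAP 6.15.1 that the symptoms listed under each IRR are coded to MedDRA preferred terms. Add two tables to Appendix 3:

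- (a) IRR component symptoms by arm.
- (b) Incidence by arm and PT, counting each subject once per symptom whether it was reported alone or within an IRR, and including the hypersensitivity-type terms (urticaria, hypotension, bronchospasm).

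Keep the existing tables, with a footnote that their symptom rows exclude IRR components.

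The cost is SAP wording, coding of symptoms already collected, and two tables. No new data or visits are needed. The IRR row and the symptom rows of table (b) will overlap by design, which the footnote should say, and AK002 symptom rates may look less favourable.
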